### **14.Provisions to Monitor the Data to Ensure the Safety of Subjects**

This study is seen as no more than minimal risk to the patient population, however, given that the patient population is at high risk for adverse outcomes, the information collected on each patient will be reviewed each time 10 patients have completed the NIRS component of the study. The neonatologists involved in the study, [name], [name] and [name], will review the data. They will also review the scientific literature at these meetings to ensure that the study protocol remains appropriate for this patient population. Any concerns or SAEs will be reported to the IRB immediately.

### **15.Withdrawal of Subjects**

If at any time there are concerns that the NIRS is interfering with routine care (although not expected to occur), the subject will be withdrawn from the research without their consent. If withdrawal from the study needs to occur, the NIRS equipment will be removed and any data collected to that point will be utilized. Collection of information will be obtained from the medical record as previously described, even if the NIRS monitoring is discontinued early. A subject can voluntarily withdrawal at any time from the study with no consequence or change in routine medical management. If a parent decides to withdraw the participant from the study, then any data that has already been collected will be kept for analysis (unless the PI is contacted as described in the next sentence). If the parent / guardian wishes to remove the data collected, then they can contact the PI , [name], at [contact] to request all data to be removed and it will be removed. No additional data will be collected.

### **16.Data Management/Confidentiality**

All data will be kept on a password protected computer in [name] office (BRF 137D), which has a locked office door and a locked ante-room door. All paper records will be kept in a locked cabinet in [name] office (BRF 137D), which has a locked office door and a locked ante-room door. All electronic data will be de-identified as soon as

## PROTOCOL TITLE:

possible with identifying information destroyed. All de-identified information will be kept until the youngest subject reaches the age of 22, as required by UNM HSC Research Policy, and then destroyed.

Each patient will be assigned a code at time of enrollment (NIRS-1, NIRS-2, etc). This will allow for de-identification of the patient. As protected health information and identifying information will be collected, this de-identification will allow for added confidentiality. The date of birth and medical record number will be the identifying information that is removed from the data collection once the study ID is assigned and the medical chart has been reviewed for the additional information (see attached excel file for additional information that will be collected). The electronic link between the study ID and the patient identifiers will be kept on [name] UNM issued computer, which is password protected. This is stored in her locked office, which also has a locked anteroom. This will not be stored in the same computer folder as any other documents pertaining to this study (it will be separated from the data). If the research team needs any of the patient information, they will be required to utilize the computer in [name] office. The data will not be publicly available unless requested with publication. No sensitive information will be collected, and a certificate of confidentiality is not required. As this is a single site study, there will be no transfer of the data required. REDCap will be used to maintain the data in a secured manner. All data will be electronically collected and stored. All data will be kept per the policy HSC-R-801 PR.1, in which research records of minors (under 18 years) must be retained until the minor turns 22 years old; thus, all data will be stored until the youngest participant has reached 22 years of age.

### **17.Data and Specimen Banking – N/A**

### **18. Risks to Subjects**

We expect the risks to the subjects to be minimal in relation to the NIRS device. The infants in this study, particularly in group 1, are at high risk of serious adverse events not related to NIRS. Specifically, this gestational age group is at high risk of death, severe brain injury, necrotizing enterocolitis, chronic lung disease, retinopathy of prematurity and sepsis. These will be included as outcome measures for the assessment, but the presence of any of these conditions would not be related to the use of NIRS.

The risks that may be present related to NIRS sensor placement include erythema and irritation of the skin around the sensor. If this is noted, the sensor will be removed. If the area appears to have erythema and/or irritation after removal, no sensor will be replaced, and the data collected to that point will be used in analysis. We will use adhesive remover or a warm moist cloth to gently remove the sensor to avoid any discomfort during this process.

As protected health information will be gathered, there is the risk for loss of privacy and/or confidentiality. We will minimize these risks by giving each participant a study ID and removing the identifiers at that time. Per policy, records of participants under the age of 18 years must be stored until the youngest participant receives 22 years of age. All records will be stored either electronically on [name] UNM issued password protected computer that is stored in her locked office, or paper copies will be stored in a locked cabinet in [name] office in BRF137D.

PROTOCOL TITLE:

Additionally, there is the possibility of unforeseen risks. Any concerns or SAE from the study will be reported to the IRB immediately.

### **19. Potential Benefits to Subjects**

The infants in this study will likely not receive direct benefit from this study. The benefit of this project will potentially be for extremely preterm infants that are born at UNMH in the future. The information obtained from this study will likely result in information that would allow the routine use of NIRS in infants born preterm. The infants in this study will likely not receive direct benefit from this study.

### **20. Recruitment Methods**

Any infant that meets the inclusion / exclusion criteria will be considered for enrollment. The mother / guardian will be approached by one of the study personnel that are included on this IRB, and the study will be discussed if they are interested in the study. The consent script has been included to show what the study personnel would verbally state to the mother / guardian. The mother / guardian may be approached at the infant's bedside or in her hospital room. If approached at the infant's bedside, the mother / guardian will be given the option to go into a family room to discuss the study further for additional privacy. The Powerchart census will be reviewed twice daily to monitor for admission of infants that would meet criteria. There will be no additional recruitment materials used for this study.

### **21. Provisions to Protect the Privacy Interests of Subjects**

To protect the privacy of the subjects in this study, consent will be obtained in the mother's hospital room if possible. However, if the mother / guardian is present at the bedside in the NICU, they will be approached and asked if the study can be discussed in a private location (utilizing a family room or conference room) or at the bedside if the mother / guardian desires. If the mother / guardian states they do not want to participate in a study, they will be informed that the infant will continue to receive all appropriate medical care and consent for use of NIRS will not be obtained.

### **22. Economic Burden to Subjects**

There is no expected economic burden to the subject. Participation in the study will result in an added mode of monitoring, at no cost to the subject. The information collected from the medical record will be obtained through electronic medical record access. There are no samples that will be obtained, and no cost expected to the participants or a 3rd party payer.

### **23. Compensation**

No compensation will be provided to infants and the mothers/guardians in the study.

### **24. Compensation for Research-Related Injury**

As this technology is used routinely in some NICUs, the study is not expected to be more than minimal risk. Therefore, no research-related injury is expected to occur, and no compensation will be offered.

PROTOCOL TITLE:

## **25. Consent Process**

Investigators included on the IRB protocol will be responsible for obtaining consent, and include [name], [name] and [name]. All are neonatologists with extensive experience in caring for this patient population as well as participating in clinical research studies. The consent process will take place in the mother's hospital room if possible, to allow for privacy. The consent process can also take place in a family room in the NICU; the consent would only be obtained at the infant's bedside if that mother / guardian requested the conversation to occur in that location. It will be stated during the consent process that participation is voluntary and will have no impact on the infant's medical care or treatment to minimize the possibility of coercion or undue influence. Once the study has been described (using the consent script that has been attached), the mother / guardian will be offered additional time to consider participation in the study. As the goal is to place the sensors within 12 hours of life, the time to consider will be dependent on the infant's age at time of initial discussion. The mother / guardian will be contacted during the study period to ensure they continue to consent to the study. During the consent process, it will be requested that the mother / guardian is able to describe the study with the sensor placement to ensure understanding.

As this study does not involve greater than minimal risk, one parent is able to give consent. If there is a guardian in place, that one guardian would be required to provide consent. This study involves neonates, so they will not be able to provide assent. Consent will be obtained for all neonates participating in the study. A partial waiver or alteration of consent is being requested in order to review the medical records to determine which infants may qualify for participation in the study.

## **26. Documentation of Consent**

We will use a consent form that is modified from the HRPO website. It has been attached for review. The signed consent forms will be stored in a locked cabinet in [name] office, which is locked and has an ante-room that is locked in non-business hours. We will obtain consent from the mother / guardian by providing them a written document that will be signed (attached). The study personnel that is obtaining consent will use the consent script to guide the review of the study (attached).

## **27. Study Test Results/Incidental Findings**

Test results will not be specifically shared with the participant's families; however, they will be able to see the monitor and the readings while at the bedside. If at any time there are significant results which support or do not support the use of the NIRS, the study will be stopped, and families will be notified immediately.

The infant will still have all routine monitoring in place with the NIRS being an additional tool. As the NIRS is a means of continuous, non-invasive monitoring of oxygenation in tissue, and the infant will have the pulse oximeter in place as part of routine monitoring, we do not expect any incidental findings.

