## 1. Objectives

The objective of this study is to obtain the cerebral regional oxygen saturation (cRSO2) in a preterm population that is born at altitude to determine if the range of “normal” values is different than those obtained at sea level. **We hypothesize that the cRSO2 will be lower than the normative values that have been previously described.** As more clinical studies are being performed, and the use of NIRS becomes more common, it is imperative that we assess if other factors such as altitude must be considered prior to general implementation.

**Aim 1:** We will prospectively obtain cRSO2 for the first 96 hours of life in infants born <32 weeks’ gestation. The data obtained will not be interrupted clinically as the clinicians will not be able to view the data obtained from the NIRS monitoring.

**Aim 2:** Outcome measures including death, intraventricular hemorrhage, necrotizing enterocolitis, sepsis, duration of supplemental oxygen required, time to taking full volume feeds via nipple, and hospital length of stay will be collected. This will be compared with the infant’s average cRSO2 as well as the fluctuation in cRSO2 that was observed. This may provide supportive evidence for clinical use of NIRS in future trials at UNMH.

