## 2. Background

Near-infrared spectroscopy (NIRS), is a technology that can provide continuous, non-invasive monitoring of oxygenation in tissue[1]. Light absorption is measured at a few discrete wavelengths which can provide information for the tissue oxygen saturation in multiple organs[2], with cerebral, renal and splanchnic oxygenation being the most commonly measured in neonates[1]. NIRS technology was first available in 1977, however different sensors and manufacturers resulted in a large range of regional oxygen saturation (RSO2), making it difficult to establish normative values within a specific population[1]. Thus, improvements in the technology has resulted in the ability to consider more clinical uses for the NIRS technology.

Infants with congenital heart disease is a population in which the NIRS technology has been applied. The use of cerebral oximetry measurement has provided the first indication of a clinical problem in 23% of the procedures in which the technology was utilized[1]. While some initial studies have shown a negative correlation between cerebral regional oxygen saturation (cRSO2) and gestational age[3], routine use in the preterm infant has not been established.

Infants born prematurely (<37 weeks’ gestation), and especially those born extremely preterm (<28 weeks’ gestation), have organs that are immature and vulnerable. There are fluctuations in cerebral blood flow due to limitations in autoregulation, which may be exacerbated by routine care of the infant[4]. Previously there was a limitation in the ability to monitor these changes in blood flow and saturations, however NIRS now provides the technology needed. There are clinical trials ongoing to assess cRSO2 immediately after birth in an attempt to improve outcomes[5] as well as monitoring in the first 72 hours of life in extremely preterm infants[4]. While these studies will likely provide support for applying NIRS as routine care for preterm infants, there is data lacking when infants are born at altitude. It is unknown if the increased altitude in places such as Albuquerque and Denver would result in a different range of expected values with NIRS monitoring. Thus, we proposed a prospective observational study in which we apply NIRS monitoring to

PROTOCOL TITLE:

infants born <32 weeks' gestation for the first 96 hours of life to assess the cRSO2 as well as outcome information for the infant.

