### **3. Study Design**

The study will be a prospective observational study, in which any infant consented to participate in the study will have the NIRS applied for the first 96 hours of life. It will be the goal to apply the NIRS sensors in the first 12 hours of life. All infants will have the same treatment if in the study, but clinicians will not be able to see the data obtained so that there is no clinical interpretation during this time.

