### **11. Multi-Site Research – N/A**

### **12. Study Procedures**

Any infant that is born at <32 weeks' gestational age and does not meet exclusion criteria as described above will be considered for the study. The mother/guardian must speak English as we do not have the resources to translate the documents, nor could we obtain consent appropriately. If an infant is born at another hospital and transferred to UNMH, they will be considered for the study only if the mother/guardian is physically present.

The study will be described following the consent script (attached) and if consent is obtained, the infant will then be given a study identifier (ex. NIRS-1). The "NIRS-1" component of the identifier will be the infant's number used so that identifying information can be removed. For sub-analysis, the infants will be divided into 3 groups to assess the impact of gestational age on the measurements. Specifically, the 3 groups will be divided into the following ages: Group 1: 23 to ≤26 weeks' gestation; Group 2: >26 weeks' gestation to ≤29 weeks' gestation; Group 3: >29 weeks' gestation to 31 6/7 weeks' gestation.

The NIRS device will be applied after the infant is admitted to the Newborn Intensive Care Unit (NICU) at UNMH (ideally within the first 12 hours of life). The device will remain in place, with routine skin care management during care times, for the first 96 hours of life and then removed. This will allow 72-96 hours of data collection, depending on the timing of the placement of the NIRS device in relation to the birth time. The SpO2 (routine oxygen saturation monitoring) information will be collected at the same time so that the relative cerebral fractional tissue oxygen extraction can be calculated. The data output will not be visible to the clinical team, so there will not be any incidental clinical interpretation of this data.

To apply the device, a trimmed piece of Mepitel (MoInlycke), which is a translucent skin dressing, will be placed with the hydrocolloid adhesive-backed NIRS sensor placed

PROTOCOL TITLE:

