directly onto the Mepitel. The sensor will then be placed with the skin dressing onto the central forehead of the infant. The sensor will be plugged in to ensure that signal strength is appropriate. There will be daily inspection of the sensor site by the research team, with the area monitored by the bedside nurse with each care-time (usually every 3 hours). The area will be monitored for erythema or irritation of the skin around the sensor, and the sensor will be removed or replaced if necessary. We will avoid lifting up the sensor unless necessary for removal or repositioning. Care will be taken to avoid pressure on top of the sensor. After the infant is 96 hours of age, the sensor will be removed. Adhesive remover or a warm moist cloth will be used to slowly remove the sensor from the skin. The sensor will then be discarded after use. The NIRS probe (circled in red) is shown below in this sample image taken from van Bel, et al[6]. Additionally, the NIRS probe is plugged into a NIRS monitor, which is then plugged into the Phillips monitor if desired. We currently have 6 of the devices which connect the NIRS to the Phillips monitor, however need to purchase the NIRS monitor and the NIRS probes.

Information will be collected from the medical record at time of enrollment as well as at the time of infant discharge. This information will include: gestational age at birth, birth weight, mode of delivery, sex of infant, maternal complications during pregnancy (including pre-eclampsia, chorioamnionitis, hypertension, diabetes, thyroid disease, and cervical insufficiency), maternal medications during pregnancy, resuscitation required at birth including if chest compressions were done, length and type of respiratory support infant required, intraventricular hemorrhage, necrotizing enterocolitis, patent ductus arteriosus and if treatment was used, chronic lung disease, retinopathy of prematurity, any surgeries that were completed during the hospitalization, sepsis, hospital length of stay, time to full volume nipple of feeds, and death if applicable. The data obtained during the NIRS recording will be collected and analyzed to determine the average cerebral regional oxygen saturation. The relative cerebral fractional tissue oxygen extraction will be calculated. The blood pressure and heart rates of each infant that are normally obtained for clinical purposes will be extracted from the patient charts during the time of the NIRS monitoring.

PROTOCOL TITLE:

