#### B. Neonates of Uncertain Viability or Nonviable Neonates

PROTOCOL TITLE:

*Complete this checklist if the subject population will include neonates of uncertain viability.*

Provide justification for each of the following:

1. Where scientifically appropriate, preclinical and clinical studies have been conducted and provide data for assessing potential risks to neonates.  
*Prior research has been conducted using the NIRS technology in this patient population. There have been minimal risks noted to the neonates that have the sensor in place. However, the use of this technology has not been reported at high altitude, which has the potential to directly impact the results.*
2. Each individual providing consent is fully informed regarding the reasonably foreseeable impact of the research on the neonate.  
*Each mother / guardian will provide consent and be fully informed. We expect there to be no direct benefit to the neonates in the study, however the results may inform future use in the NICU that may become routine.*
3. Individuals engaged in the research will have no part in determining the viability of a neonate.  
*The use of this technology will not impact the viability of the neonate, and the research team will not be determining the viability of the neonate in relation to this study.*
4. The research holds out the prospect of enhancing the probability of survival of the neonate to the point of viability, and any risk is the least possible for achieving that objective, or, the purpose of the research is the development of important biomedical knowledge which cannot be obtained by other means and there will be no added risk to the neonate resulting from the research  
*The results from this study have the potential to impact the routine use of this technology in the NICU and may have the ability to note if/when an infant is having an acute change in cerebral blood flow which may reflect an intraventricular hemorrhage. The purpose of this research cannot be obtained by other means and there will be no added risk to the neonate resulting from the research.*

Verify each of the following:

1. The research will not terminate the heartbeat or respiration of the neonate  
 True  
 False
2. There will be no added risk to the neonate resulting from the research  
 True

PROTOCOL TITLE:

False

---

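### Section 27 leaves the NIRS readings visible to families at the bedside, which in practice undercuts the masking of clinicians promised in Sections 1, 3 and 12

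*Combined protocol and SAP*

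**What the plan says.** Masking is stated three times. Under Aim 1 in Section 1, "the clinicians will not be able to view the data obtained from the NIRS monitoring". Section 3 gives the purpose: "clinicians will not be able to see the data obtained so that there is no clinical interpretation during this time". Section 12 repeats it: "The data output will not be visible to the clinical team".

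Section 27 says that results will not be specifically shared with families, and then adds: "however, they will be able to see the monitor and the readings while at the bedside".

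Section 12 also describes the set-up. The probe feeds a NIRS monitor, "which is then plugged into the Phillips monitor if desired". The research team inspects the sensor site daily, and the bedside nurse looks at the area at each care-time, usually every 3 hours.

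The same paragraph of Section 27 requires the study to stop, at any time, if there are significant results for or against NIRS. Section 6 places the analysis after enrolment is complete. Sections 7 and 14 provide a review every 10 infants. Section 7 frames it as a safety review, and Section 14 adds a review of the scientific literature and reporting of concerns to the IRB.

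**The concern.** The study aims to describe cRSO2 in preterm infants at altitude under usual care, and then to relate each infant's average and fluctuation to later outcomes. Both aims need readings that did not influence care while they were being recorded. Masking the clinical team is how the protocol secures this.

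If the display is open to families at the bedside, the masking depends on staff not looking at a screen beside the infant they are tending, and on parents not mentioning what they see. If care changed in response, the recorded cRSO2 would partly be a treated value. The altitude range could then be shifted, and the association with outcomes could be distorted. Exposure of this kind cannot be undone or reliably reconstructed once the recordings have been made.

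**Working it through.** The plan has no figure to reproduce here. The check sets the passages side by side and adds two short sums.

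**1. Who is masked and who can see.** Sections 1, 3 and 12 mask clinicians or the clinical team. Section 27 gives sight of the monitor and readings to families. No sentence gives clinicians access, so the sentences can all be true only if something separates what a family sees from what staff at the same bedside see.

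**2. Is a separation described?** The text examined mentions no cover, blanked screen, log-only mode or instruction against relaying values. It does not say whether values appear on the Phillips monitor when the optional link is used. The consent form and script, which are attachments, and Section 9 (Resources Available) were not in the text examined.

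**3. How often are staff there?** Section 12 expects 72 to 96 hours of recording, with nurse checks usually every 3 hours.
- 72 / 3 = 24 care-times
- 96 / 3 = 32 care-times

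This counts opportunities per infant, assuming that the usual interval holds. It does not count readings seen or acted on.

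**4. Route to bias.** Section 13 averages cRSO2 for each infant and computes fractional extraction as (SpO2 − rScO2)/SpO2. A change in care prompted by a reading could alter the average, the fluctuation and the extraction. To size the effect one would need the share of readings noticed, the chance of a response and the effect of that response. The documents give none of these, so neither size nor direction can be stated.

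**5. What hiding the values would risk.** With no visible values, lost signal might be noticed only at the research team's daily inspection. Section 4 admits to the final sample only infants with at least 48 hours of monitoring.
- Margin with 72 hours of recording: 72 − 48 = 24 hours
- Margin with 96 hours of recording: 96 − 48 = 48 hours

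If the 48 hours means usable signal, which Section 4 does not specify, then at the short end one unnoticed gap between daily inspections could use up the whole margin. The remedy must allow for this.

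**6. The stopping clause.** Section 27 does not say whether the results are the study's own or published ones. If they are the study's own, the clause fits poorly with Section 6, which analyses data after enrolment, and with Section 13, which plans no interim analysis. If they are outside evidence, Section 14's literature review is the natural route, but Section 27 does not refer to it.

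**The case against.** The strongest reply is that nothing here is contradictory as written. The masking sentences concern clinicians and the visibility sentence concerns families. The Phillips link may serve only to capture data alongside the simultaneous SpO2, and a cover could be described in material outside the text examined. Section 27 itself expects no incidental findings, because routine monitoring including pulse oximetry stays in place. All of this is fair. It rules out calling the passages a literal contradiction. It does not explain how a screen that families can read is kept from staff at the same bedside.

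A reader might go further and infer that staff would act on what they saw. The documents do not support that. The checklist in Section 38, part B, says NIRS may reveal "an acute change in cerebral blood flow which may reflect an intraventricular hemorrhage", but the context is possible future routine use, not conduct in this study. The Background's account of problems first detected by cerebral oximetry comes from infants with congenital heart disease. The assurance at consent that participation does not affect care is given to minimise coercion or undue influence, so it is weak ground for claiming that a promise would be broken.

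On stopping, a reader might infer that the plan contains unadjusted interim testing, or that it will end short of 100 infants with a less precise range. Neither follows. No interim test is planned, the clause names no point at which the study would stop, and outside evidence is an open reading. A review every 10 infants and a route to the IRB already exist. What remains is that Section 27 is not tied to them.

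**Conclusion.** The masking concern holds as a practical conflict. Followed as written, Section 27 defeats a design feature that the protocol states three times, and no safeguard is described. Bedside staff have roughly 24 to 32 scheduled opportunities per infant to see an open display. The resulting bias in Aims 1 and 2 is possible but cannot be sized or signed from the documents. The conclusion assumes that the display families see is the NIRS reading itself, which is the natural meaning of the sentence, and that no shielding is set out in material outside the text examined. It should be corrected before enrolment, because the remedy is cheap and later repair is not possible.

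The stopping clause is a secondary point. It is unclear about the source of the results and poorly joined to the existing reviews, but no particular harm can be shown from the documents.

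**What to change.** **Masking.**
- Reconcile Section 27 with Sections 1, 3 and 12 by removing the sentence on family visibility.
- State in Section 12 that numeric cRSO2 values are covered or blanked at the bedside and only logged, including on any Phillips monitor link. Logging of cRSO2 and of the simultaneous SpO2 is unchanged.
- Keep a signal-quality indicator visible without cRSO2 values, or check the logged signal at the daily inspection, in view of the 48-hour rule in Section 4.
- Check the consent form and script, and align what families are told about the display.

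**Stopping clause.** Reconcile Section 27 with Sections 6, 7 and 14. State that the study's own cRSO2 and outcome results are not tested before enrolment is complete, and that any early stop comes through the existing 10-infant safety and literature review.

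**Cost.** The changes need some rewording, a screen cover or display setting, and a check of the consent documents. Families lose the chance to watch the reading. Signal loss could go unnoticed for longer unless the signal check is adopted. The sample size and the schedule of reviews do not change.
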